### **4.3 STUDY TREATMENT**

The investigational medicinal products (IMPs) for this study are obinutuzumab, *rituximab*, polatuzumab vedotin, and lenalidomide.

#### **4.3.1 Formulation, Packaging, and Handling**

##### **4.3.1.1 Obinutuzumab**

Obinutuzumab will be provided as a single-dose, sterile liquid formulation in a 50-mL glass vial containing 1000 mg/40 mL of obinutuzumab. In addition to the drug substance, the liquid is also composed of histidine, trehalose, and poloxamer 188. For information on the formulation and handling of obinutuzumab, see the pharmacy manual and the Obinutuzumab Investigator's Brochure (oncology) and local prescribing information.

##### **4.3.1.2 Rituximab**

*Rituximab will be supplied by the Sponsor as an IMP. Rituximab is packaged in 10-mL (100-mg) and 50-mL (500-mg) single-dose, pharmaceutical-grade glass vials at a concentration of 10 mg/mL of protein. The antibody is formulated for IV injection as a sterile product in a solution of sodium chloride (pH 6.5) containing polysorbate 80 and sodium citrate. For information on the formulation and handling of rituximab, see the pharmacy manual and the Rituximab Investigator's Brochure.*

##### **4.3.1.3 Polatuzumab Vedotin**

Polatuzumab vedotin will be supplied by the Sponsor as a sterile, white to off-white, preservative-free lyophilisate in single-use vials. For information on the formulation and

handling of polatuzumab vedotin, see the pharmacy manual and the Polatuzumab Vedotin Investigator's Brochure.

#### **4.3.1.4 Lenalidomide**

Lenalidomide will be supplied by the Sponsor as 5-, 10-, 15-, and 20-mg capsules.

Female caretakers of patients taking lenalidomide who are of childbearing potential should not handle or administer lenalidomide unless they are wearing gloves. Lenalidomide should be stored at room temperature away from direct sunlight and should be protected from excessive heat and cold.

For information on the formulation and handling of lenalidomide, see the local prescribing information for lenalidomide.

#### **4.3.2 Dosage, Administration, and Compliance**

Patients enrolled in the dose-escalation phase or the expansion phase will receive six 28-day cycles of induction treatment with obinutuzumab *or rituximab*, polatuzumab vedotin, and lenalidomide. When study treatments are given on the same day, they will be administered sequentially in the following order: lenalidomide, *obinutuzumab or rituximab*, and polatuzumab vedotin.

Patients with DLBCL who achieve a CR or PR at EOI will receive post-induction treatment (referred to as consolidation) with lenalidomide and *rituximab*, and patients with FL who achieve a CR, PR, or SD at EOI will receive post-induction treatment (referred to as maintenance) with lenalidomide and obinutuzumab. When study treatments are given on the same day, lenalidomide will be administered prior to obinutuzumab *or rituximab*.

Post-induction treatment should start 8 weeks ( $\pm 1$  week) after Day 1 of the final cycle of induction and will continue until disease progression or unacceptable toxicity for up to 2 years for maintenance treatment or *6 months* for consolidation treatment.

Treatment regimens are summarized in [Table 1](#), [Table 2](#), [Table 4](#), and [Table 5](#) for R/R FL patients and [Table 6](#), [Table 7](#), [Table 9](#), and [Table 10](#) for R/R DLBCL patients (see Section 3.1) and depicted in [Figure 4](#). All eligible patients in both dose-escalation and expansion phases should receive induction and post-induction (if indicated) therapy.

Premedication and treatment for TE prophylaxis should be administered as described in Section [4.3.2.5](#).

Any overdose or incorrect administration of any of the study treatments should be noted on the Study Drug Administration electronic Case Report Form (eCRF). Adverse events associated with an overdose or incorrect administration of any of the study treatments should be recorded on the Adverse Event eCRF.

#### **4.3.2.1 Obinutuzumab**

[figure not shown]
Obinutuzumab will be administered by IV infusion at an absolute (flat) dose of 1000 mg on Days 1, 8, and 15 of the first cycle and on Day 1 of each subsequent cycle during induction treatment, and on Day 1 of every other month (i.e., every 2 months) during maintenance treatment (eligible patients with FL only). A month is defined as 28 days.

Obinutuzumab should be administered as an IV infusion through a dedicated line in an environment in which full resuscitation facilities are immediately available and under the close supervision of an experienced physician. Obinutuzumab infusions will be administered according to the instructions outlined in [Figure 5](#) and [Figure 6](#). For patients with bulky lymphadenopathy, the infusion may be given slowly over a longer period of time, or the dose may be split and given over more than 1 day.

No dose modification for obinutuzumab is allowed. Guidelines for treatment delays or discontinuation are provided in Section [5.1.7](#).

Premedication with a corticosteroid, antihistamine, and analgesic/antipyretic, as outlined in Section [4.3.2.5](#), is required to reduce the incidence and severity of IRRs. For anaphylaxis precautions, see [Appendix 8](#).

**Figure 5 Guidelines for Obinutuzumab Infusions: First Infusion**

[figure not shown]

IRR = infusion-related reaction.

a All patients should receive full premedication with an oral corticosteroid, antihistamine, and oral analgesic/antipyretic prior to the first obinutuzumab infusion. Refer to Section 4.3.2.5 for details.

b Supportive treatment should include acetaminophen/paracetamol and an antihistamine such as diphenhydramine, if not administered within the previous 4 hours. Intravenous saline may be indicated. For bronchospasm, urticaria, or dyspnea, patients may require antihistamines, oxygen, corticosteroids (e.g., 100 mg oral prednisone or equivalent), and/or bronchodilators. For anaphylaxis precautions, see Appendix 8.

**Figure 6** *Guidelines for Obinutuzumab Infusions: Second and Subsequent Infusions*

IRR =infusion-related reaction; q30 =every 30.

a Patients should receive full premedication with an oral corticosteroid, antihistamine, and oral analgesic/antipyretic prior to the obinutuzumab infusion. In the case of a recurrent Grade 3 IRR, obinutuzumab may be discontinued at the discretion of the investigator, following an individual benefit–risk assessment.

b Patients who experience wheezing, urticaria, or other symptoms of anaphylaxis must receive full premedication prior to all subsequent doses.

### **4.3.2.2 Rituximab**

*Rituximab will be administered by IV infusion at the dose of 375 mg/m^2 on Day 1 of Cycles 1–6 during induction treatment and on Day 1 of every other month (i.e., every 2 months) during consolidation treatment for patients with R/R DLBCL.*

*Body surface area (BSA) will be determined at screening and should be used to calculate the dose of rituximab throughout the study unless the patient's weight increases or decreases by >10% from screening, in which case BSA should be recalculated and used for subsequent dosing. In obese patients (defined as body mass index  $\geq 30$  kg/m^2), there is no BSA cap and actual body weight, not adjusted weight, is recommended. Empiric dose adjustment for obese patients may be implemented per institutional guidelines.*

*The infusion of rituximab may be split over 2 days if the patient is at increased risk for an IRR (high tumor burden or high peripheral lymphocyte count). Administration of rituximab may be continued on the following day, if needed, for patients who experience an adverse event during the rituximab infusion.*

*If a dose of rituximab is split over 2 days, both infusions must occur with appropriate premedication (see Section 4.3.2.5) and at the first infusion rate (see Table 12).*

*Rituximab infusions will be administered according to the instructions in Table 12. During the treatment period, rituximab must be administered to patients in a setting where full emergency resuscitation facilities are immediately available. Patients should be under close supervision of the investigator at all times.*

*Rituximab should be administered as a slow IV infusion through a dedicated line. After the end of the first infusion, the IV line or central venous catheter should remain in place for  $\geq 2$  hours in order to administer IV drugs, if necessary. If no adverse events occur after 2 hours, the IV line may be removed or the central venous catheter may be de-accessed. For subsequent infusions, the IV line or central venous catheter should remain in place for at least 1 hour after the end of the infusion. If no adverse events occur after 1 hour, the IV line may be removed or the central venous catheter may be de-accessed.*

**Table 12 Administration of First and Subsequent Infusions of Rituximab**

First Infusion (Day 1 of Cycle 1)	Subsequent Infusions

 
• Begin infusion at an initial rate of 50 mg/hr.
 
• If no infusion-related or hypersensitivity reaction occurs, increase the infusion rate in 50-mg/hr increments every 30 minutes to a maximum of 400 mg/hr.
 
• If a reaction develops, stop or slow the infusion. Administer medications and supportive care in accordance with institutional guidelines. If the reaction has resolved, resume the infusion at a 50% reduction in rate (i.e., 50% of rate being used at the time when the reaction occurred).
 
	
 
• If the patient experienced an infusion-related or hypersensitivity reaction during the prior infusion, use full premedication, including 100 mg of prednisone/prednisolone or 80 mg of methylprednisolone or equivalent (until no further IRR occurs); begin infusion at an initial rate of 50 mg/hr; and follow instructions for first infusion.
 
• If the patient tolerated the prior infusion well (defined by an absence of Grade 2 reactions during a final infusion rate of <math>\geq</math> 100 mg/hr), begin infusion at a rate of 100 mg/hr.
 
• If no reaction occurs, increase the infusion rate in 100-mg/hr increments every 30 minutes to a maximum of 400 mg/hr.
 
• If a reaction develops, stop or slow the infusion. Administer medications and supportive care in accordance with institutional guidelines. If the reaction has resolved, resume the infusion at a 50% reduction in rate (i.e., 50% of rate being used at the time when the reaction occurred).
 

No dose modification for rituximab is allowed. Guidelines for treatment delays or discontinuation are provided in Section 5.1.6.

Premedication with a corticosteroid, analgesic/antipyretic, and antihistamine, as outlined in Section 4.3.2.5, is required to reduce the incidence and severity of IRRs. For anaphylaxis precautions, see Appendix 8.

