**Table 13 Premedication**

Timepoint	Patients Requiring Premedication	Premedication	Administration
Cycle 1, Day 1	
 
All patients
 
	
 
Oral corticosteroida
 
	Complete ≥ 1 hour prior to obinutuzumab or rituximab infusion
	
 
All patients
 
	
 
Antihistamine drugb
 
Oral analgesic/antipyreticc
 
	Administer ≥ 30 minutes prior to obinutuzumab or rituximab infusion
	
 
Patients at risk for TLS (e.g., because of bulky disease or renal impairment [creatinine clearance < 70 mL/min])
 
	
 
Allopurinol or suitable alternative, such as rasburicase, along with adequate hydration
 
	Administer prior to obinutuzumab or rituximab infusion
Cycle 1, Days 8 and 15  Cycles 2 and Beyond, Day 1	
 
Patients with no IRR during the previous infusion
 
	
 
Oral analgesic/anti-pyreticc
 
	Administer at least 30 minutes prior to obinutuzumab infusion. For patients receiving rituximab, premedication may be omitted at the investigator's discretion.
	
 
Patients with Grade 1 or 2 IRR during the previous infusion
 
	
 
Antihistamine drugb
 
Oral analgesic/antipyreticc
 
	Administer ≥ 30 minutes prior to obinutuzumab or rituximab infusion
	
 
Patients with Grade 3 IRR, wheezing, urticarial, or other symptoms of anaphylaxis during the previous infusion
 
Patients with bulky disease
 
	
 
Oral corticosteroida
 
	Complete ≥ 1 hour prior to obinutuzumab or rituximab infusion
			
 
Antihistamine drugb
 
Oral analgesic/antipyreticc
 

	
 
Patients still at risk for TLS
 
	
 
Allopurinol or suitable alternative, such as rasburicase, along with adequate hydration
 
	Administer prior to obinutuzumab or rituximab infusion

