### **5.1.2.1 Infusion-Related Reactions**

Acute IRRs are very common in patients receiving rituximab (occurring in  $\geq 10\%$  of patients) based on clinical trial experience. However, serious IRRs are uncommonly reported (occurring in  $\geq 1$  of 1,000 and  $< 1$  of 100 patients) and are rarely fatal (occurring in  $\geq 1$  of 10,000 and  $< 1$  of 1,000 patients). Most IRRs occur with the first administration of rituximab. Most IRRs are mild to moderate in severity (Grades 1 or 2) and can be managed by slowing or stopping the rituximab infusion. IRRs can be severe and, in rare cases, can result in death. Rituximab-induced IRRs consist of a cluster of symptoms and signs occurring during or within 24 hours of a rituximab infusion that may be related to cytokine release and/or other chemical mediators, and these acute IRRs overlap with “cytokine release syndrome.” Anaphylactic and other hypersensitivity reactions have been reported following rituximab administration, and clinical manifestations of these reactions are similar to cytokine release syndrome. In contrast to cytokine release syndrome, true hypersensitivity reactions typically occur within minutes of starting the rituximab infusion.

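### After a Grade 2 rituximab reaction, and possibly a Grade 1 reaction, Tables 12 and 13 give different corticosteroid premedication for the next infusion

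*Combined protocol and SAP*

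**What the plan says.** Section 4.3.2.2 directs that rituximab be infused according to Table 12. In the column for infusions after the first, Table 12 states: "If the patient experienced an infusion-related or hypersensitivity reaction during the prior infusion, use full premedication". It then names a corticosteroid, prednisone/prednisolone or methylprednisolone or an equivalent, as part of that premedication, to be kept up until reactions stop. The same bullet restarts the infusion at 50 mg/hr. The next bullet starts at 100 mg/hr "If the patient tolerated the prior infusion well (defined by an absence of Grade 2 reactions during a final infusion rate of" at least 100 mg/hr).

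Section 4.3.2.5 directs that patients be premedicated as set out in Table 13. For Day 1 of Cycle 2 onward, Table 13 sorts patients by what happened at the previous infusion:

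- After no reaction it lists an oral analgesic/antipyretic, and adds "For patients receiving rituximab, premedication may be omitted at the investigator's discretion".
- The row "Patients with Grade 1 or 2 IRR during the previous infusion" lists an antihistamine and an oral analgesic/antipyretic, timed before obinutuzumab or rituximab.
- An oral corticosteroid appears in the row that covers "Patients with Grade 3 IRR, wheezing, urticarial, or other symptoms of anaphylaxis during the previous infusion" and patients with bulky disease.

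Section 5.1.2.1 says of rituximab reactions: "Most IRRs are mild to moderate in severity (Grades 1 or 2"). It gives no percentage. It also says that most reactions come with the first administration.

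**The concern.** Two tables in current force address the same decision: what to give before the next rituximab infusion when the last one caused a mild or moderate reaction. One includes a corticosteroid and the other does not list one. Grade 1 and 2 reactions are also the common kind, by the protocol's own account.

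The first consequence is for conduct. A site that follows one table to the letter departs from the other, and no sentence says which governs. The second is for the safety data. Section 5.2.5 makes infusion-related reactions selected adverse events. If steroid cover after a first reaction depends on which table a site reads, the rate of repeat reactions mixes two practices.

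**Working it through.** No figure is involved, so the check sets the two tables side by side for a later rituximab infusion.

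| What happened at the previous infusion | Table 12 | Table 13 | Do they agree? |
|---|---|---|---|
| No reaction | Full premedication not triggered | Analgesic/antipyretic, which may be omitted for rituximab | No conflict |
| Grade 1, no bulky disease, no signs of anaphylaxis | Ambiguous (see below) | Antihistamine and analgesic/antipyretic | Depends on how Table 12 is read |
| Grade 2, no bulky disease, no signs of anaphylaxis | Full premedication with corticosteroid | Antihistamine and analgesic/antipyretic | Conflict |
| Grade 1 or 2 with bulky disease, wheezing, urticaria or other signs of anaphylaxis | Full premedication with corticosteroid (Grade 1 ambiguous, as above) | Corticosteroid, antihistamine and analgesic/antipyretic | No conflict if Table 12's reaction bullet is applied |
| Grade 3 | Full premedication with corticosteroid | Corticosteroid, antihistamine and analgesic/antipyretic | No conflict on the corticosteroid |

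**Grade 2.** The reaction bullet of Table 12 applies, because it has no grade limit. The well-tolerated bullet cannot apply, because it requires that no Grade 2 reaction occurred. The corticosteroid is therefore called for in Table 12 and absent from the matching row of Table 13.

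**Grade 1.** A Grade 1 reaction is still a reaction, so the first bullet fits. It is also compatible with the absence of Grade 2 reactions, so the second bullet fits if the final rate reached 100 mg/hr. The two bullets give different starting rates, 50 and 100 mg/hr, so they cannot both be followed. If the first governs, Table 12 conflicts with Table 13. If the second governs, Table 12 does not call for a corticosteroid and there is no conflict.

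**Does either table yield?** Table 13 is not confined to obinutuzumab: its Grade 1 or 2 row names rituximab in the timing column, and the no-reaction row has its own rituximab sentence. The sentence after Table 12 on premedication refers to Section 4.3.2.5, which leads to Table 13. It does not amend the corticosteroid instruction inside Table 12.

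**Size.** Rituximab goes to the DLBCL patients only. Section 6.1 plans 12–18 in dose escalation and 40 in expansion: 12 + 40 = 52 to 18 + 40 = 58 patients. Section 5.1.2.1 puts acute reactions at 10% or more. Assuming that category applies here, 0.10 × 52 = 5.2 and 0.10 × 58 = 5.8, so at least five or six patients would be expected to have an acute reaction of some grade. The documents give no split by grade, no repeat-reaction rate and no proportion with bulky disease, so the number of discordant infusions cannot be computed.

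**The case against.** The strongest reply has four parts.

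- **Table 12 can be read as grading reactions.** If its two bullets are alternatives, a Grade 1 reaction can fall under the well-tolerated bullet and outside full premedication. This stands, and it limits the clear conflict to Grade 2. It does not remove it.
- **Table 13 forbids nothing.** It lists who requires which premedication, so adding a corticosteroid would not breach it. That is fair as to wording. But a site relying on Table 13 alone would omit a drug that Table 12 tells it to give, and that is enough for practice to diverge.
- **Steroid exposure was never meant to be uniform.** Section 4.3.2.3 leaves corticosteroids before polatuzumab vedotin, given the same day, to the physician. This stands as a limit on the consequence for the data. It does not explain why two required schedules differ.
- **The consequence is small.** Grade 3 and 4 infusion reactions are excepted from the dose-limiting toxicity definition, and adverse events are summarised descriptively. This also stands.

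Three stronger readings are tempting, and the documents do not support them.

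- A reader might infer that the sentence after Table 12 makes a corticosteroid mandatory at every infusion, against the permission in Table 13 to omit premedication. That sentence requires it only as Section 4.3.2.5 outlines, so it defers to Table 13. After a reaction-free infusion the two tables do not conflict.
- A reader might infer that every rituximab patient with a Grade 1 or 2 reaction is affected. Table 13 still gives a corticosteroid when there is bulky disease or when wheezing, urticaria or other signs of anaphylaxis occurred.
- A reader might infer that the conflict runs through all later induction and consolidation infusions. Table 12 looks only at the infusion just before and stops once no further reaction occurs, and Section 5.1.2.1 says most reactions come with the first administration.

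**Conclusion.** The inconsistency is real and narrow. For a later rituximab infusion after a Grade 2 reaction, in a patient without bulky disease and without wheezing, urticaria or other signs of anaphylaxis, Table 12 calls for a corticosteroid and Table 13 does not list one. For Grade 1 the answer turns on an overlap inside Table 12 that the protocol does not settle. Both tables bind and neither has precedence.

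The effect is possible uneven steroid cover between sites after the same reaction, and so some loss of clarity in the data on repeat reactions. It is confined to the DLBCL group and its frequency is unknown. No dose-escalation decision, sample-size figure or efficacy estimate is shown to depend on it. This is a minor point, worth correcting because it is a safety instruction and easy to repair. The conclusion assumes that both tables are meant as written.

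**What to change.** The sponsor must reconcile Tables 12 and 13 so that one premedication instruction, set out by reaction grade, applies to later rituximab infusions. Three things need settling:

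- whether a corticosteroid is part of premedication after a Grade 2 reaction;
- which bullet of Table 12 governs after a Grade 1 reaction;
- which table Sections 4.3.2.2 and 4.3.2.5 should point to for premedication, with the other table cross-referring to it.

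The content of the rule is the sponsor's clinical decision, and none is proposed here. The cost is an edit to the two tables and their cross-references in the next amendment, with a note to sites. No change to the sample size or analyses is needed.

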#### 4.3.2.3 Polatuzumab Vedotin

For R/R FL, during the dose-escalation phase, the dose of polatuzumab vedotin for each patient will depend on dose assignment (1.4 or 1.8 mg/kg). During the expansion phase, the dose of polatuzumab vedotin for each patient will depend on the RP2D established during the dose-escalation phase. For R/R DLBCL, during the dose-escalation phase and the expansion phase, the dose of polatuzumab vedotin will be fixed at 1.8 mg/kg. Polatuzumab vedotin will be administered by IV infusion on Day 1 of each cycle, during induction treatment only.

The patient's weight obtained during screening (Days -28 to -1) should be used for dose determination for all treatment cycles. If the patient's weight within 96 hours prior to Day 1 of a given treatment cycle is > 10% from the weight obtained during screening, the new weight should be used to calculate the dose. The weight that triggered a dose

adjustment will be taken as the new reference weight for future dose adjustments. All subsequent doses should be modified accordingly.

After reconstitution with Sterile Water for Injection (SWFI) and dilution into IV bags containing isotonic sodium chloride solution (0.9% NaCl), polatuzumab vedotin will be administered by IV infusion using dedicated standard administration sets with 0.2- or 0.22- $\mu$ m in-line filters at a final polatuzumab vedotin concentration determined by the patient-specific dose. Compatibility of polatuzumab vedotin with IV bags, infusion lines, filters, and other infusion aids has been established with items made of specific materials of construction. Please consult the pharmacy manual and the Polatuzumab Vedotin Investigator's Brochure for a list of compatible materials and specific dose preparation instructions.

The initial dose will be administered to patients who are well hydrated over 90 ( $\pm$ 10) minutes. Premedication (e.g., 500–1000 mg of oral acetaminophen or paracetamol and 50–100 mg diphenhydramine as per institutional standard practice) may be administered to an individual patient before administration of polatuzumab vedotin. Administration of corticosteroids is permitted at the discretion of the treating physician. If IRRs are observed with the first infusion in the absence of premedication, premedication must be administered before subsequent doses.

The polatuzumab vedotin infusion may be slowed or interrupted for patients experiencing infusion-associated symptoms. Following the initial dose, patients will be observed for 90 minutes for fever, chills, rigors, hypotension, nausea, or other infusion-associated symptoms. If prior infusions have been well tolerated, subsequent doses of polatuzumab vedotin may be administered over 30 ( $\pm$ 10) minutes, followed by a 30-minute observation period after the infusion.

Guidelines for dosage modification and treatment interruption or discontinuation are provided in Section [5.1.7](#).

